### 13. Purpose—in nontechnical, lay language

Summarize the purpose and objectives of this protocol, including any related projects, in one short paragraph.

**The purpose of this study is to evaluate the efficacy of the Aerodentis system for orthodontic tooth movement in an open label, two-arms, non-inferiority clinical study. This open label, two-arm study will follow 45 patients for up to fifteen (15) months. Thirty participants will wear the Aerodentis device, and fifteen participants will wear Invisalign. Patients will be assigned to participate in the treatment group using the Aerodentis device at home for 10 hours daily or in the control group using**

clear correctors for the duration of up to 15 months. Outcome assessments will be performed every 4 weeks. Assessments will include tooth movement and quality of life assessments.

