#### **15. Participants (Screening and Selection)**

a. How many participants are to be enrolled at UAB? 45, 30 active and 15 control

If multi-center study, total number at all centers: \_\_\_\_\_

b. Describe the characteristics of anticipated or planned participants.

Sex: male and female

Race/Ethnicity: all races

Age: 12-60 with adult dentition (permanent teeth)

Health status: medically fit and well

*Note. If data from prior studies indicate differences between the genders or among racial/ethnic groups in the proposed research or if there are no data to support or to negate such differences, Phase 3 clinical trials will be required to include sufficient and appropriate entry of gender and racial/ethnic subgroups so that trends detected in the affected subgroups can be analyzed. If ethnic, racial, and gender estimates are not included in the protocol, a clear rationale must be provided for exclusion of this information. If prior evidence indicates that the results will not show gender or racial differences, researchers are not required to use gender or race/ethnicity as selection criteria for study participants. They are, however, encouraged to include these groups. See Section II. Policy of the NIH POLICY AND GUIDELINES ON THE INCLUSION OF WOMEN AND MINORITIES AS SUBJECTS IN CLINICAL RESEARCH – Amended, October, 2001) for further details.*

c. From what population(s) will the participants be derived?

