Statistical Analysis Plan

Title of Research: Aerodentis Clinical Trial: Assessment of the Efficacy of

Orthodontic Tooth Movement Using the Aerodentis System

UAB IRB Protocol #: F160418007

Principal Investigator: [name] [name], BDS, MScD, PhD.

Co-investigators: [name], DMD, PhD

[name], DDS

Sponsor: Dror Orthodesign Ltd.

[name]

[name]

[name]

Statistical Considerations

Overview and Rationale for Primary Parameter

The aims of this trial are to assess the safety and efficacy of the Aerodentis system in producing tooth movement. Safety is measured by absence of root resorption while efficacy is typically measured by various parameters relating to tooth movement. Because tooth movement is highly variable between individuals, treatment success is not usually contingent on a specific amount of movement over time. To this end we specify the primary endpoint, achieving score <1mm in Little's index

Design

Historical controls will be utilized as a comparator group. This historical data will be generated using the same inclusion/exclusion criteria as the proposed prospective single arm study. The historical patient population will be derived from the study sites participating in this prospective study. The study inclusion/exclusion criteria will be applied to consecutive patients treated with clear correctors that have the potential for complete datasets (as defined by the study protocol).

The use of single arm, open label trial with historical controls is supported when a device technology is well developed and the subject of interest is well understood^[1]. Orthodontic treatment of this patient population (i.e., use of mechanical force) is well developed and understood. In addition, the primary

Page 1 of 3

Version Date: 9/27/2016

^[1] Draft Guidance for Industry, Clinical Investigators, and Food and Drug Administration Staff Design Considerations for Pivotal Clinical Investigations for Medical Devices, published August 15, 2011.

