endpoints of success are Objective Performance Criteria (OPC) (use of impressions to objectively measure tooth movement and Little's index scoring and independent radiographic evaluation of tooth resorption). The effectiveness OPC in the treatment of this patient population is a summative Little's index score of <1.5mm. The safety OPC is to allow for no tooth root resorption. The use of this study design is supported both by proposed FDA Gudiance⁵ and recent FDA approvals of devices with a high risk profile^[2]

Safety Analysis Set

The safety analysis set will consist of all patients from whom dental plaster impressions were taken for the purpose of treatment with Aerodentis.

Full Analysis Set

Primary efficacy analysis will be assessed using the Full Analysis Set (FAS). The FAS will consist of patients from the intent to treat (ITT) cohort who started treatment and have at least one post-baseline assessment, and have no major protocol violation as determined by blind review.

Missing Data:

Missing data will be handled for imputation the primary endpoint data for FAS subjects. Subjects with no post-baseline assessment will be imputed as failures and will not be included in the FAS population. The MMRM model (Mixed-effect Model for Repeated Measures), which is based on MAR (missing at random) assumption will be applied to all the subjects of the FAS population. Sensitivity analyses will be applied for testing the effect of the imputation on the treatment effect. This will show the influence of the imputation on the study results.

Per Protocol Analysis Set

Efficacy analyses will also be done on the Per Protocol subset. Per Protocol subset include all FAS subjects who completed the study according to the protocol with no protocol deviations.

Missing Values: Only observed data will be used in the Per Protocol Analysis Set; i.e. missing data will not be imputed.

Endpoints

Safety

The safety endpoints are adverse events, whether or not treatment related. Included will be amount of root repsorption, measured by comparing x-rays before, mid-point and after treatment

Primary Efficacy

The primary endpoint will be to evaluate the degree of tooth movement. Treatment success will be defined using the Little's Index and when a score does not summative exceed 1.5mm (<1.5mm)

YGgDw&usg=AFQjCNGQWAFNwDj6XKq5ZVay8hssRm9lzA&bvm=bv.51156542,d.cWc

Page 2 of 3

Version Date: 9/27/2016

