^[2] Campbell, Greg Some Considerations for Medical Devices: Historical Controls and Performance Goals, FDA-NIH Science of Small Clinical Trials Course. November 27-28, 2012

https://www.google.com/url?sa=t&rct=j&g=&esrc=s&source=web&cd=15&cad=rja&ved=0CEIQFjAEOAo&url=https%3A%2F%2 Fevents-support.com%2FDocuments%2FCampbell.pdf&ei=OL4dUvnoLMK9sAT7-

This is a reasonable endpoint as the results are comparable to other successful aligner studies. In addition, studies to long term stability have used 2mm or less as an acceptable outcome of success post orthodontic treatment.

Invisalign® treatment in the anterior region: were the predicted tooth movements achieved? Krieger E¹, Seiferth J, Marinello I, Jung BA, Wriedt S, Jacobs C, Wehrbein H. http://www.ncbi.nlm.nih.gov/pubmed/22890691

How well does Invisalign work? A prospective clinical study evaluating the efficacy of tooth movement with Invisalign. **Kravitz** 2009

http://www.ncbi.nlm.nih.gov/pubmed/19121497

Semin Orthod. 1999 Sep;5(3):191-204.

Stability and relapse of mandibular anterior alignment: University of Washington studies. Little RM.

Br J Orthod. 1990 Aug;17(3):235-41.

Stability and relapse of dental arch alignment.

Little RM1.

Sample Size Considerations

The planned sample size is 40 subjects. The tested group will include 40 subjects.

Study Hypotheses

We will have demonstrated success if the summative Little's index score will achieve score <1.5mm.

Statistical Analysis

All measured variables and derived parameters will be tabulated by descriptive statistics.

For categorical variables summary tables will be provided giving sample size, absolute and relative frequency and 95% CI (Confidence Interval) for proportions.

For continuous variables summary tables will be provided giving sample size, arithmetic mean, standard deviation, median, minimum and maximum and 95% CI (Confidence Interval) for means of variables.

Complete individual listings of all data represented in the CRF will be provided as an appendix. All calculated and derived variables will be listed as well.

All tests will be two-tailed, and a p value of 5% or less will be considered statistically significant. All statistical analyses will be performed and data appendices will be created using the SAS® system Version 9.1.3 or higher.

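### The SAP plans a single arm of 40 with historical controls, the protocol a two-arm non-inferiority study of 30 v 15; the Little's index threshold differs within the SAP, and no margin, success proportion or contrast is given

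*SAP*

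**What the plan says.** **Design.** Protocol section 13 says the device will be evaluated "in an open label, two-arms, non-inferiority clinical study", and section 15.d repeats this. SAP, Design, says "Historical controls will be utilized as a comparator group" and adds: "This historical data will be generated using the same inclusion/exclusion criteria as the proposed prospective single arm study".

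**Numbers.** Protocol section 15.a: "45, 30 active and 15 control". SAP, Sample Size Considerations: "The planned sample size is 40 subjects. The tested group will include 40 subjects". The SAP gives no number of historical controls.

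**Threshold.** SAP, Overview and Rationale for Primary Parameter: "we specify the primary endpoint, achieving score <1mm". SAP, Design: "The effectiveness OPC in the treatment of this patient population is a summative Little's index score of <1.5mm". SAP, Study Hypotheses: "We will have demonstrated success if the summative Little's index score will achieve score <1.5mm". The Primary Efficacy paragraph also uses 1.5 mm.

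**Allocation.** Protocol section 15.d describes systematic assignment, with controls drawn from patients already treated on site and from new patients who ask for aligners. Section 16.a says participants are picked at random for the two groups.

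**Analysis.** The SAP lists descriptive statistics with 95% CIs for proportions and means, two-tailed tests at 5%, and an MMRM under Missing Data. It defines no contrast between device and control.

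**The concern.** A plan must fix who is compared with whom, how many patients there are, and what result counts as success. Here the two documents answer the first two differently, and the third is incomplete. The protocol's non-inferiority claim has no margin and no analysis in the SAP to carry it. The SAP's own claim rests on a score cut-off with two values and no share of patients who must reach it. Both the cut-off and the share could therefore be settled after the data are seen.

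The conflict over allocation adds to this. If controls are already in treatment or have chosen aligners, a difference between groups may reflect case mix, and a margin alone would not turn the comparison into a sound non-inferiority test.

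**Working it through.** **1. The documents side by side**

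| Item | Protocol | SAP |
|---|---|---|
| Arms | Two, concurrent aligner control | One, historical clear-corrector controls |
| Treated with the device | 30 | 40 |
| Total | 45 | 40 (historical controls not counted) |
| Claim | Non-inferiority | Success on a score threshold |
| Margin | None | None |
| Success proportion to exceed | None | None |
| Threshold | None given | <1 mm and <1.5 mm |

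**2. Can either sample size be reproduced?** No. The only design input given is the two-sided 5% level. Power, success rates, SD, margin and dropout are absent. 40/(1 - 0.10) = 44.4, which rounds up to 45, and 30/(1 - 0.25) = 40, but no dropout rate is stated and the 45 includes 15 controls. These are coincidences, not derivations.

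The figures below are illustrations. All rates, goals and margins are assumed, with no dropout and success counted per patient.

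**3. Two arms, 30 v 15, equal true success p.** Half-width = 1.96 × sqrt[p(1 - p)(1/30 + 1/15)]. At p = 0.80: 1.96 × sqrt(0.16 × 0.10) = 1.96 × 0.1265 = 0.248. Power is by enumeration of all 31 × 16 outcomes. Non-inferiority is claimed when the Miettinen-Nurminen score statistic at a 20-point margin exceeds 1.96.

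| True success | Half-width (points) | Power, 20-point margin |
|---|---|---|
| 70% | 28 | 34% |
| 80% | 25 | 43% |
| 90% | 19 | 57% |
| 95% | 14 | 72% |

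**4. Non-random controls.** Same enumeration and margin. A comparable control succeeds in 80% and the device in 60%, so the device is truly 20 points worse. Case mix then moves the observed controls' rate.

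| Controls' success after case mix | False non-inferiority claims |
|---|---|
| 80% (no shift) | 3% |
| 70% (lowered by 10 points) | 12% |
| 90% (raised by 10 points) | 0.3% |

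The documents do not say which direction applies.

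**5. Single arm of 40.** The smallest count whose exact (Clopper-Pearson) two-sided 95% lower limit exceeds the goal is 27 for 50%, 31 for 60% and 34 for 70%. If true success is 80%, the chance of reaching those counts is 98%, 73% and 29%. The verdict therefore depends heavily on a goal that the SAP does not state.

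**6. Per patient or mean?** Three features of the SAP point to a per-patient outcome: success is defined on a score, subjects without a post-baseline assessment are treated as failures, and CIs for proportions are planned. No sentence states it, however, and an MMRM models repeated continuous scores and does not fit a single binary outcome.

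**The case against.** The strongest defence is that this is a small, largely descriptive study, that a sample size rationale may sit in the attached Aerodentis Proposal (Protocol section 23), and that per-patient success is clear enough from context. The proposal was not among the documents reviewed, so it cannot be said that no rationale exists anywhere. Even so, a rationale there would leave the protocol and SAP describing different trials. The descriptive defence fails because the protocol claims non-inferiority and the SAP speaks of demonstrating success.

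On the per-patient point the defence largely stands. A reader might infer that the threshold is meant for a group mean, since the SAP mentions an MMRM and CIs for means. The text does not support this: the CIs for means apply to every continuous variable, the MMRM appears only under Missing Data, and the failure rule makes sense only for a yes/no outcome. What remains is that the unit should be stated and the MMRM given a fitting role.

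A reader might also infer that the control group makes a false non-inferiority claim likely. The documents do not support that either. Allocation is contradictory rather than known to be non-random, and case mix could lower the false-claim rate as well as raise it.

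Nor do the documents show that 30 v 15 is too small in itself. With no margin or expected rate, adequacy cannot be judged; at 95% success and a 20-point margin, power would be 72%.

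**Conclusion.** The point holds and should be settled before outcomes are analysed. The conflicts in design, treated number, total and claim, and the two thresholds, are facts of the text and need no assumption. So is the absence of a margin from both documents, and of a success proportion and between-group contrast from the SAP. It follows that neither non-inferiority nor demonstrated success can be concluded as planned.

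The numerical consequences are conditional on the assumed rates, margin and goals, and show only how much turns on what is unstated. The allocation conflict is a further reason why the non-inferiority claim is unsupported at present; the size and direction of any bias are unknown.

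**What to change.** **Under either design.** Reconcile both documents to one design, one sample size with its rationale and one Little's index threshold. State that success is judged per patient at one named assessment. Limit the MMRM to the continuous score as a secondary analysis, and state a rule for missing final scores in the binary endpoint.

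**If the protocol's design stands.** Replace 40 in the SAP with 30 + 15, state the precision this delivers, and reconcile Protocol sections 15.d and 16.a on allocation. Keep the term non-inferiority only if allocation is random and a margin is justified in advance. The claim is then judged by the lower limit of a two-sided 95% score CI for the difference in success (device minus control), which must lie above minus the margin. Otherwise remove the term and report the difference with its 95% CI as a non-randomised, descriptive estimate, with pre-treatment Little's index by group and an estimate adjusted for it.

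**If the SAP's design stands.** Remove non-inferiority and the 30/15 split from the protocol, and state the success proportion that the lower 95% limit must exceed. Hold any historical comparison to the same conditions: stated control number and contrast, pre-treatment Little's index shown and adjusted for, labelled non-randomised, and no non-inferiority claim.

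**Cost.** Rewriting the SAP and amending protocol wording; a weaker claim if controls are not randomised; and obtaining pre-treatment scores for controls already in treatment. The SAP's design also costs historical chart abstraction and the 15 concurrent controls. If 40 is kept, it needs 40 - 30 = 10 more treated patients than the protocol allocates; restating the number as 30 avoids this.

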**Exclusion:**

- 1. Any medical or dental condition that, in the opinion of the investigator, could negatively affect study results during the expected length of the study. Conditions can include poor oral hygiene, extensive dental treatments, or periodontal disease.**
- 2. Patient is currently using any investigational drug or any other investigational device.**
- 3. Patient plans to relocate or move during the treatment period.**
- 4. Allergic to acetaminophen (use of aspirin or non-steroidal anti-inflammatory drugs is excluded for patients while on the study).**
- 5. Use of bisphosphonates (osteoporosis drugs) during the study.**
- 6. Pregnant females. Orthodontic treatment is not advised in pregnant females. Hormonal changes may affect tooth movement, the unborn fetus can be affected during mandatory x-rays, and unexpected complication in pregnancy may arise that could negatively affect orthodontic treatment.**
- 7. Patients that, in the opinion of the investigator orthodontist, are unable to comply with safe and effective device use.**
- 8. Patients that are likely unwilling to be compliant with device use, as determined by the questionnaire for compliance.**

d. If participants will comprise more than one group or stratification, describe each group (e.g., treatment/intervention, placebo, controls, sham treatment) **and** provide the number of participants anticipated in each group.

**This is an open label, two-arm, non-inferiority study. Patients will be systematically assigned to a treatment group (wearing the Aerodentis device) or control group (wearing clear aligners).**

Participants from the control group come from both current patients treated on site and new patients coming into the orthodontics clinics, requesting treatment with clear aligners.

- e. Indicate which, if any, of the special populations listed below will be involved in the protocol. Include the Special Populations Review Form (SPRF) if indicated.
- Pregnant Women: Attach [SPRF—Pregnant Women, Fetuses, Neonates/Nonviable Neonates](#)
  - Fetuses: Attach [SPRF—Pregnant Women, Fetuses, Neonates/Nonviable Neonates](#)
  - Neonates/Nonviable Neonates: [SPRF—Pregnant Women, Fetuses, Neonates/Nonviable Neonates](#)
  - Prisoners: Attach [SPRF—Prisoners](#)
  - Minors (<18 years old): Attach [SPRF—Minors](#)
  - Employees or students at institution where research conducted
  - Persons who are temporarily decisionally impaired

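### The protocol declares a non-inferiority study, but the SAP contains no non-inferiority hypothesis, margin, between-group interval or decision rule

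*SAP*

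**What the plan says.** The protocol states the aim twice. Section 13 says the purpose is to "evaluate the efficacy of the Aerodentis system for orthodontic tooth movement in an open label, two-arms, non-inferiority clinical study". Section 15.d repeats: "This is an open label, two-arm, non-inferiority study". Section 13 gives the group sizes: "Thirty participants will wear the Aerodentis device, and fifteen participants will wear Invisalign".

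The SAP describes a different framework and does not use the term non-inferiority:

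- **Design:** a single prospective arm. "Historical controls will be utilized as a comparator group".
- **Sample Size Considerations:** "The planned sample size is 40 subjects. The tested group will include 40 subjects". No number of historical controls is given.
- **Study Hypotheses:** "We will have demonstrated success if the summative Little's index score will achieve score <1.5mm".
- **Statistical Analysis, summaries:** categorical variables are tabulated with "absolute and relative frequency and 95% CI (Confidence Interval) for proportions", and continuous variables with 95% intervals for means.
- **Statistical Analysis, tests:** "All tests will be two-tailed, and a p value of 5% or less will be considered statistically significant".

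A mixed model for repeated measures is named under Missing Data, without a treatment contrast or a decision rule.

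**The concern.** A non-inferiority conclusion needs a null hypothesis shifted by a margin or, equivalently, a rule that compares a confidence bound for the between-group difference with that margin. Neither document contains one. The only written criterion for any test is a significance level. With no shifted null stated, the natural default is a test of no difference, and that test does not address whether Aerodentis is acceptably close to clear aligners.

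The primary conclusion is at stake. In an open-label study with no written rule, the criterion can be chosen after results are known. With groups this small, a non-significant difference is likely even when the new device is materially worse. If that were taken as support for non-inferiority, imprecise data would favour the claim.

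**Working it through.** **The plan's own figures.** Neither 40 (SAP) nor 45 = 30 + 15 (protocol) can be reproduced. The documents give no margin, expected success rate, standard deviation, power or dropout allowance.

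**What a non-inferiority analysis needs, against what is written:**

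| Element | In the documents |
|---|---|
| Non-inferiority aim | Protocol 13 and 15.d only |
| Shifted null hypothesis | None |
| Margin | None |
| Interval for Aerodentis minus clear aligner | None; SAP intervals are descriptive summaries of proportions and means |
| Rule comparing a bound with the margin | None |
| Test criterion | Two-tailed, p of 5% or less, no null named |
| Success statement | Score below 1.5 mm; no comparator, required proportion or error rate |

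**How often a real deficit would be non-significant.** From the documents: 30 v 15, two-sided 5%. Assumed: control success pC of 70%, 80% or 90%; true Aerodentis success pC − d; success analysed as a binary outcome. The probability is the sum over all outcomes (a of 30, b of 15) of Bin(a; 30, pC − d) × Bin(b; 15, pC), counting those with Fisher p above 0.05.

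| True deficit d | pC 70% | pC 80% | pC 90% |
|---|---|---|---|
| 10 points | 93.5% | 92.7% | 94.0% |
| 15 points | 89.1% | 87.1% | 86.1% |
| 20 points | 82.4% | 79.3% | 74.8% |
| 30 points | 61.0% | 58.2% | 47.7% |

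With an uncorrected chi-square test the 20-point row is 76.6%, 73.0% and 66.2%. With the SAP's 40 tested patients and an assumed 40 controls, the Fisher figures at 20 points are 63.2%, 59.2% and 46.6%.

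**One possible result.** Aerodentis 17/30 (56.7%), clear aligner 12/15 (80.0%); difference −23.3 points; Fisher p = 0.19. The Wilson limits are 0.392 to 0.726 and 0.548 to 0.930. The Newcombe lower bound is −0.233 − √[(0.567 − 0.392)² + (0.930 − 0.800)²] = −0.451. The result is non-significant, yet compatible with a deficit of about 45 points.

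**A margin-based rule on the same data.** Conclude non-inferiority only if the Newcombe lower 95% bound exceeds minus the margin. Same enumeration, 30 v 15:

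- True deficit equal to the margin (margins 10-30 points): passes 2.6-3.4% of the time.
- Equal true rates, assumed 20-point margin: passes 34.3%, 44.4% and 65.4% of the time for pC of 70%, 80% and 90%.

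**What 80% power would need.** At 2:1, one-sided 2.5% and equal true rates, controls = (1.960 + 0.842)² × pC(1 − pC) × (1 + 1/2) / margin². For a 20-point margin:

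- pC 70%: 7.849 × 0.21 × 1.5 / 0.04 = 61.8, so 62 controls and 186 in total.
- pC 80%: 47.1, so 48 and 144.
- pC 90%: 26.5, so 27 and 81.

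For 30:15, the smallest margin supported at 80% power is 2.802 × √[pC(1 − pC)(1/15 + 1/30)], or about 41, 35 and 27 points.

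**The case against.** The strongest reply is that the significance sentence is a general convention, placed beside the software version, and not the primary decision rule. It fixes sidedness and level and names no null. The SAP locates success in its Study Hypotheses, as a performance criterion for a single-arm study, and names no between-group test. This is fair, and it shows that the sentence itself need not go: a two-sided 5% level corresponds to the two-sided 95% interval used in a standard non-inferiority analysis. It does not fill the gap, because the success statement has no required proportion or error rate, and the SAP still calls its historical controls a comparator group.

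Three stronger readings are tempting, and none is supported:

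- **That the plan will treat p above 5% as non-inferiority.** No section says so. The documents merely fail to exclude it.
- **That stating a margin would not help while the p-value sentence stands.** A margin with its shifted null or confidence-bound rule would work alongside that sentence.
- **That the criterion also misleads in the other direction, by declaring Aerodentis significantly worse when it is within an acceptable limit.** At 30 v 15, no outcome is both significantly worse by Fisher and a pass on the Newcombe rule at margins of 10, 15, 20, 30 or 40 points.

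It is also true that the probabilities rest on assumed control rates, and that the 40 v 40 case rests on an assumed control number.

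**Conclusion.** The concern holds as an omission. The protocol declares non-inferiority, and the SAP supplies none of the elements needed to conclude it, so the plan followed as written cannot support its declared conclusion. That finding rests on the text alone.

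The size of the risk is conditional. With control success of 70-90% and 30 v 15, a true 20-point deficit is non-significant by Fisher in 75-82% of trials, whereas a confidence-bound rule with a 20-point margin would wrongly pass about 3%. The contrast matters only if non-significance were read as non-inferiority. Non-significance is not the likelier result in every case: at a 30-point deficit with 90% control success it is 48%.

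This should be settled before outcome data are seen, because it determines what the primary result can mean.

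**What to change.** 1. Reconcile the comparator first: the protocol has a clear-aligner arm of 15, the SAP a single arm with historical controls. Group sizes need the same reconciliation. An unadjusted interval does not deal with bias from non-concurrent controls. If the single-arm design is the intended one, the SAP needs a stated performance goal with an exact test, and the non-inferiority label must be reconciled with that.
2. If non-inferiority is kept, add to the SAP's Study Hypotheses and Statistical Analysis: a margin justified before data are seen; the difference in success proportion (Aerodentis minus clear aligner) with a two-sided 95% confidence interval, for example Newcombe; non-inferiority concluded only if the lower bound lies above minus the margin; and a statement that p above 5% is not evidence of non-inferiority. The two-tailed 5% sentence can stay for other comparisons.
3. Otherwise, remove the non-inferiority term from protocol sections 13 and 15.d, and report the difference with its 95% interval as estimation only.

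The cost is SAP wording, plus a protocol wording change under option 3. No procedures or patients are added by the rule itself. The downside is a lower chance of a favourable result: about 34-65% under equal success rates of 70-90%, an assumed 20-point margin and 30 v 15. Reaching 80% power at that margin would take about 81 to 186 patients, so the sponsor should weigh options 2 and 3 with that in view.
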